### **4.2 Scientific Rationale for Study Design**

This study is designed to characterize the association between CT identified epicardial adipose tissue and HFS mapping identified GP sites in the right and left atrium. Given the evidence that GP ablation can be beneficial for patients undergoing catheter ablation for atrial fibrillation, all patients will undergo GP ablation following mapping in addition to standard pulmonary vein isolation. The hierarchical relationship within the network of cardiac GPs is unknown as is the optimal order of GP ablation. Given equipoise in the order of GP ablation, we will equally allocate the site of initial ablation between the 8 major GP ablation locations.

### **4.3 End of Study Definition**

A participant is considered to have completed the study if he or she has completed all phases of the study including the last visit.

## **STUDY POPULATION**

### **4.4 Inclusion Criteria**

In order to be eligible to participate in this study, an individual must meet all of the following criteria:

1. Provision of signed and dated informed consent form
2. Stated willingness to comply with all study procedures and availability for the duration of the study
3. Male or female, aged >18 years
4. History of AF with plan to undergo catheter ablation

### **4.5 Exclusion Criteria**

An individual who meets any of the following criteria will be excluded from participation in this study:

1. Contraindication or unwillingness to undergo CT imaging or catheter ablation.
2. Pregnancy or lactation

### **4.6 Screen Failures**

Screen failures are defined as participants who consent to participate in the clinical trial but are not subsequently randomly assigned to the study intervention or entered in the study. A minimal set of screen failure information is required to ensure transparent reporting of screen failure participants, to meet the Consolidated Standards of Reporting Trials (CONSORT) publishing requirements and to respond to queries from regulatory authorities. Minimal information includes demography, screen failure details, eligibility criteria, and any serious adverse event (SAE).

### **4.7 Strategies for Recruitment and Retention**

Participants will be recruited from the investigator's clinical practice. We anticipate an accrual rate of approximately 4 subjects per month. Long term follow-up for the study will include the standard of care monitoring of patients following catheter ablation.

[figure not shown]
## STUDY INTERVENTION

### 4.8 Study Intervention(s) Administration

#### 4.8.1 *Study Intervention Description*

All patients will have GP mapping performed using the Nicolet (Natus) Cortical Stimulator (see attached) with 12V output at 20Hz frequency with 10ms pulse duration with at least 3grams of contact force. Stimulation will be provided for up to 10 seconds or until vagal response is noted (>2s ventricular asystole, AV block, or R-R interval increase by at least 50%). Natus stimulator had FDA clearance (K072964) for cortical stimulation. Prior to ablation, baseline ear vagus nerve stimulation will be performed via stimulation of bilateral cyma concha to document response using Parasym tragal stimulator (IDE information attached). Ablation of mapped GPs will be performed using standard ablation catheter with routine approaches to ablation energy delivery and monitoring (see below flowchart). Following ablation of each GP, local HFS will be repeated in all GP regions and ear vagus nerve stimulation will be repeated via bilateral cyma concha. After all GP are ablated, all patients be given IV atropine (0.04mg/kg max: 4mg) to assess global vagal tone. Following this, patients will undergo pulmonary vein isolation using standard equipment and techniques.

Devices will be obtained from the manufacturer (Natus and Parasym respectively) and will be stored in a secured laboratory space. No particular temperature or climate requirements are present for either device. All devices will be labeled according to the manufacturer guidance and will be returned to the manufacturer in the event of any device failure. Devices will be stored and managed in compliance with OCR guidelines.

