### **2.2.1 Clinical Adverse Event Profile**

Potential complications of catheter ablation of atrial fibrillation include bleeding, vascular injury, cardiac perforation, atrioesophageal fistula formation, phrenic nerve injury, bradycardia, arrhythmia induction, myocardial infarction, and stroke. These complications are related to the insertion of catheters from the femoral veins into the heart and across the intra-atrial septum to the left atrium as well as the delivery of radiofrequency energy in the left atrium. We do not anticipate the mapping portion of the procedure, which will be performed with a standard ablation catheter, to confer significant additional risk. The most likely increased risk from high frequency stimulation is the induction of atrial fibrillation, which is common as part of routine ablation procedures and does not pose significant risk. We do not anticipate these risks to be significantly modified by the additional ablation targeting ganglionated plexi, which are located in regions frequently targeted in ablation of atrial fibrillation and atypical atrial flutters.

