## **2.3 Risk/Benefit Assessment**

### **2.3.1 Known Potential Risks**

As discussed above, potential risks of ablation of ganglionated plexi include the risk factors associated with catheter ablation for atrial fibrillation as discussed above. An additional theoretical risk includes increased sinus rates following vagal denervation, which has been described as transient in the literature and not seen in our own experience. Potential risks of ear stimulation include local discomfort or skin irritation/burns. Potential risks of high frequency stimulation include pain, which will not be perceived given the use of general anesthesia, and the induction of atrial fibrillation, which routinely occurs during atrial fibrillation ablations.

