### 3 STUDY OBJECTIVES AND ENDPOINTS

OBJECTIVES	ENDPOINTS	JUSTIFICATION FOR ENDPOINTS
Primary		
	
 
Successful identification of GP signals by high frequency stimulation and anatomic correlation between these points and CT identified epicardial adipose tissue within 3 pixels (0.625x3=1.875mm).
 
	This correlation will allow us to determine the ability of pre-procedural CT imaging to predict GP location.
Secondary		
To assess the effects of GP ablation on local HFS response and global vagal stimulation in order to characterize the neural pathways connecting GPs	
 
Elimination of local of HFS response following GP ablation
 
Elimination of global vagal response to non-invasive ear stimulation
 
	
	
 
Amplitude, duration, and fractionation of signals at sites with HFS responses and successful HFS elimination
 
	

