## 7 STATISTICAL CONSIDERATIONS

### 7.1 Statistical Hypotheses

- Primary Efficacy Endpoint(s): We anticipate anatomic correlation between CT identified epicardial adipose tissue within 3 pixels ( $0.625 \times 3 = 1.875\text{mm}$ ) of an endocardial mapping point where HFS confirmed a vagal response consistent with ganglionated plexus innervation.
- Secondary Efficacy Endpoint(s): Acute procedural success defined by elimination of ear vagus nerve stimulation response will be achievable in all patients.

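### AV block with no qualifying condition counts as a vagal response during 20 Hz atrial stimulation, so atrial capture or AF alone can make a site HFS-positive

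*Combined protocol and SAP*

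**What the plan says.** Section 4.8.1 sets the mapping stimulus at "12V output at 20Hz frequency with 10ms pulse duration with at least 3grams of contact force". A train lasts at most 10 seconds and may end sooner, since it runs only "until vagal response is noted (>2s ventricular asystole, AV block, or R-R interval increase by at least 50" percent. This one sentence of the protocol both ends the train and supplies the only definition of a positive HFS response.

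On the effect of the stimulus on the atrium, section 2.2.1 says: "The most likely increased risk from high frequency stimulation is the induction of atrial fibrillation". Section 2.3.1 again lists "the induction of atrial fibrillation, which routinely occurs during atrial fibrillation ablations". Eligibility (section 4.4) asks only for "History of AF with plan to undergo catheter ablation".

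The response feeds two endpoints:
- **Primary.** Section 7.1 relates CT-identified fat to "an endocardial mapping point where HFS confirmed a vagal response consistent with ganglionated plexus innervation".
- **Secondary.** The first secondary endpoint in section 3 is "Elimination of local of HFS response following GP ablation". Section 6.1 also uses it for acute procedural efficacy.

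After each GP is ablated, section 4.8.1 repeats local HFS in every GP region.

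**The concern.** Two of the three alternatives have a numeric threshold on the ventricular rhythm. AV block has none, and because the list is joined by 'or' it is enough by itself. The visible text does not require sinus rhythm, does not time pulses to atrial refractoriness, and does not ask whether the train captured the atrium.

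AV block means that atrial beats fail to reach the ventricle. In sinus rhythm that can indicate a vagal effect. In an atrium driven fast, or in AF, some beats fail to conduct whatever the vagus is doing. Starting every train in sinus rhythm would not remove the problem, because the train itself can cause the capture or the AF.

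Three results are exposed:
- **CT correlation.** The reference standard may include sites that have no GP.
- **Local elimination.** If a lesion abolishes local capture, capture-driven block disappears whether or not the ganglion was reached. If AF or capture persists, block persists even where denervation succeeded.
- **Network objective.** In regions not yet ablated, continuing capture could hide a remote effect of ablation elsewhere.

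**Working it through.** The plan gives no figure for this point, so there is none to reproduce. Steps 1 and 2 check the mechanism. Steps 3 and 4 show how the error would propagate, on assumed values.

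**1. Stimulus (section 4.8.1).** Interval = 1000/20 = 50 ms. Rate = 20 × 60 = 1200 per minute. A full train has 20 × 10 = 200 pulses.

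**2. Conduction.** If the atrium followed every pulse, a ventricular rate of 200/min would mean 1200/200 = 6:1 conduction, and 300/min would mean 1200/300 = 4:1. The atrium need not follow every pulse. Assume instead capture or AF at 300 to 400/min and a conducted ventricular rate of 120 to 200/min (neither is in the documents). The blocked share is 1 − conducted/atrial:
- 1 − 200/300 = 0.33
- 1 − 120/400 = 0.70

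Non-conducted beats are therefore expected with no vagal input. The 33% to 70% is a share of beats within a captured train. It is not a share of sites misclassified.

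**3. Baseline map.** Let π be the share of tested sites that are truly GP, s the HFS sensitivity (assumed 0.9), and f the rate of capture- or AF-related AV block scored as positive at non-GP sites (assumed). The false share of positives is (1 − π)f / [πs + (1 − π)f]. For π = 0.2 and f = 0.05 this is 0.04/(0.18 + 0.04) = 0.18.

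| π | f = 5% | f = 10% | f = 25% |
|---|---|---|---|
| 0.1 | 33% | 50% | 71% |
| 0.2 | 18% | 31% | 53% |
| 0.5 | 5% | 10% | 22% |

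**4. Retest after ablation.** Let q be the share of baseline positives that are artefact, d the true denervation rate, and c the share of artefact sites whose AV block is gone at retest. Apparent elimination is (1 − q)d + qc. Take c = 1 if every lesion loses capture, and c = 0 if AF or capture always persists.

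| q | d | c = 1 | c = 0 |
|---|---|---|---|
| 0.2 | 50% | 0.8×0.5 + 0.2 = 60% | 0.8×0.5 = 40% |
| 0.5 | 50% | 0.5×0.5 + 0.5 = 75% | 0.5×0.5 = 25% |
| 0.2 | 80% | 0.8×0.8 + 0.2 = 84% | 0.8×0.8 = 64% |
| 0.5 | 80% | 0.5×0.8 + 0.5 = 90% | 0.5×0.8 = 40% |

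The apparent rate is above d when c > d and below it when c < d. The c = 0 column is not a floor, because persisting AF could also keep a truly denervated site scored as responding. The documents give no value for π, f, q, d or c.

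**The case against.** The best reply is that the section speaks of a vagal response, and section 7.1 adds that it must be consistent with GP innervation. An experienced operator would not call every dropped atrial beat in AF a vagal response. Practice may well be better than the wording. But neither phrase tells the person scoring how to separate the two, and unwritten judgement is a weak basis for a reference standard.

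A second reply is that other checks exist. Section 7.1 defines acute success by loss of the ear-stimulation response, and atropine tests global vagal tone after all GPs are ablated. That is correct, but neither check validates an individual HFS site.

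Third, the flowchart and the stimulator attachment cited in section 4.8.1 are not shown. A synchronisation or capture rule there would answer much of this, and a cross-reference would then be enough.

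Three stronger readings are tempting but not supported:
- **That the elimination endpoint is biased towards success.** This needs lesions to abolish capture, which the protocol does not state. Persisting AF pushes the other way.
- **That a third or more of sites are misclassified.** The documents do not say how often trains capture, or how many sites are positive on AV block alone.
- **That elimination should be judged only on retests with capture.** That conditions on a post-ablation result. If lesions do abolish capture, it would discard the most completely ablated sites.

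**Conclusion.** The point holds as a fault in the endpoint definition and should be corrected. Read as written, section 4.8.1 lets atrial capture or AF alone produce an HFS-positive site, under a stimulus that the protocol expects to induce AF. This can contaminate the reference standard of the primary endpoint and can distort local elimination in either direction.

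The mechanism rests on the protocol's own stimulation rate and AF statements, together with the limited conduction capacity of the AV node. The frequency and net direction are unknown. The false shares in the working (5% to 71%) and the shifts in apparent elimination show sensitivity to assumed inputs and are not estimates for this trial. Loss of capture in a lesion is likewise an assumption.

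**What to change.** State the scoring definition for the endpoints separately from the sentence that ends a train, and specify:

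1. When the atrium is captured or in AF, AV block alone does not make a site positive. One of the two ventricular-interval criteria already in section 4.8.1 is required. AV block alone counts only for non-conducted sinus P waves.
2. Rhythm and capture (yes/no) are recorded for every baseline and repeat train, read from the electrograms and entered prospectively.
3. A train that ended on AV block before an interval criterion could appear is indeterminate, not negative. The number of such trains is reported.
4. All retests stay in the local-elimination endpoint. Results by capture status are a sensitivity analysis.

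The cost is a paragraph of wording and two fields per train. Some sites will become negative or indeterminate, which matters with 19 patients. The scoring will also lean more on the R-R criterion, for which section 4.8.1 names no reference interval; that should be stated at the same time. No change to stimulation, to the rule for ending a train, or to clinical management is proposed.

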#### 4.9 Study Intervention Compliance

Following the ablation procedure, compliance will only be necessary for follow-up visits, which will be performed per clinical routine.

## **5 STUDY INTERVENTION DISCONTINUATION AND PARTICIPANT DISCONTINUATION/WITHDRAWAL**

### **5.1 Participant Discontinuation/Withdrawal from the Study**

Participants are free to withdraw from participation in the study at any time upon request.

An investigator may discontinue or withdraw a participant from the study for the following reasons:

- Pregnancy
- Significant non-compliance with follow-up visits
- If any clinical adverse event (AE), laboratory abnormality, or other medical condition or situation occurs such that continued participation in the study would not be in the best interest of the participant
- If the participant meets an exclusion criterion (either newly developed or not previously recognized) that precludes further study participation

The reason for participant discontinuation or withdrawal from the study will be recorded on the Case Report Form (CRF). Subjects who sign the informed consent form and are randomized but do not undergo ablation may be replaced. Subjects who sign the informed consent form and are randomized and undergo ablation, and subsequently withdraw, or are withdrawn or discontinued from the study, will not be replaced.]

### **5.2 Lost To Follow-Up**

A participant will be considered lost to follow-up if he or she fails to return for two scheduled visits and is unable to be contacted by the study site staff.

The following actions must be taken if a participant fails to return to the clinic for a required study visit:

- The site will attempt to contact the participant and reschedule the missed visit within 3 months and counsel the participant on the importance of maintaining the assigned visit schedule and ascertain if the participant wishes to and/or should continue in the study.
- Before a participant is deemed lost to follow-up, the investigator or designee will make every effort to regain contact with the participant (where possible, 3 telephone calls and, if necessary, a certified letter to the participant's last known mailing address or local equivalent methods). These contact attempts should be documented in the participant's medical record or study file.
- Should the participant continue to be unreachable, he or she will be considered to have withdrawn from the study with a primary reason of lost to follow-up.

## 6 STUDY ASSESSMENT AND PROCEDURES

### 6.1 Efficacy Assessments

- Elimination of local HFS response and ear vagus nerve stimulation will determine acute procedural efficacy
- Loop recorder or ambulatory monitors interrogations to evaluate presence and burden of atrial fibrillation
- History to identify symptomatic atrial fibrillation and to identify episodes of AF that may have been vagally mediated

### 6.2 Safety and Other Assessments

- Physical examination will be performed following the ablation procedure to identify any procedural complications including vascular or neurological injury.
- Repeat examination and history will be performed at follow-up visit to identify any potential procedural complications.

### 6.3 Adverse Events and Serious Adverse Events

#### 6.3.1 ***Definition of Adverse Events (AE)***

An adverse event (AE) is any untoward medical occurrence associated with the use of an intervention in humans, whether or not considered intervention related. Intercurrent illnesses or injuries should be regarded as adverse events.

A pre-existing condition should be recorded as an adverse event if the frequency, intensity or the character of the condition changes.

#### 6.3.2 ***Definition of Serious Adverse Events (SAE)***

Serious Adverse Events (SAE)

Adverse events are classified as serious or non-serious. A serious adverse event is any AE that, in the view of either the investigator or the sponsor, is:

- fatal
- life-threatening
- requires or prolongs hospital stay
- results in persistent or significant disability or incapacity
- a congenital anomaly or birth defect
- an important medical event when the event does not fit the other outcomes, but the event may jeopardize the patient and may require medical or surgical intervention (treatment) to prevent one of the other outcomes.
- required intervention to prevent permanent impairment or damage (for devices only)

Important medical events are those that may not be immediately life threatening but are clearly of major clinical significance. They may jeopardize the subject and may require intervention to prevent one of the other serious outcomes noted above. For example, drug overdose or abuse, a seizure that did not result in in-patient hospitalization, or intensive treatment of bronchospasm in an emergency department would typically be considered serious.

### **6.3.3      *Classification of an Adverse Event***

#### **6.3.3.1      *Severity of Event***

For adverse events (AEs) not included in the protocol defined grading system, the following guidelines will be used to describe severity.

- Mild – Events require minimal or no treatment and do not interfere with the participant’s daily activities.
- Moderate – Events result in a low level of inconvenience or concern with the therapeutic measures. Moderate events may cause some interference with functioning.
- Severe – Events interrupt a participant’s usual daily activity and may require systemic drug therapy or other treatment. Severe events are usually potentially life-threatening or incapacitating. Of note, the term “severe” does not necessarily equate to “serious”.

#### **6.3.3.2      *Relationship to Study Intervention***

All adverse events (AEs) must have their relationship to procedure assessed by the clinician who examines and evaluates the participant based on temporal relationship and his/her clinical judgment. The degree of certainty about causality will be graded using the categories below. In a clinical trial, the study product must always be considered.

- Related – The AE is known to occur with the GP mapping or ablation, there is a reasonable possibility that the procedure caused the AE, or there is a temporal relationship between the procedure and event. Reasonable possibility means that there is evidence to suggest a causal relationship between the procedure and the AE.
- Not Related – There is not a reasonable possibility that the administration of the procedure caused the event, there is no temporal relationship between the procedure and event onset, or an alternate etiology has been established.

#### **6.3.3.3      *Expectedness***

The primary investigator will be responsible for determining whether an adverse event (AE) is expected or unexpected. An AE will be considered unexpected if the nature, severity, or frequency of the event is not consistent with the risk information previously described for the procedure.

#### **6.3.4 Time Period and Frequency for Event Assessment and Follow-Up**

Safety will be assessed by monitoring and recording potential adverse effects using the CTCAE grading system at each study visit. Participants will be monitored by medical histories, physical examinations, and loop recorder interrogations. If CTCAE grading does not exist for an adverse event, the severity of mild, moderate, severe, life-threatening, and death, corresponding to Grades 1-5, will be used whenever possible.

At each contact with the subject, the investigator will seek information on adverse events by non-directive questioning and, as appropriate, by examination. Adverse events may also be detected when they are volunteered by the subject during the screening process or between visits, or through physical examination, laboratory test, or other assessments. Information on all adverse events will be recorded in the source documentation. To the extent possible, adverse events will be recorded as a diagnosis and symptoms used to make the diagnosis recorded within the diagnosis event.

As much as possible, each adverse event or follow-up information will be evaluated to determine:

1. Severity grade (CTCAE Grade 1-5)
2. Duration (start and end dates)
3. Relationship to the study treatment or process – [Reasonable possibility that AE is related: No (unrelated/ not suspected) or Yes (a suspected adverse reaction)]. If yes (suspected) - is the event possibly, probably or definitely related to the investigational treatment?
4. Expectedness to study treatment or process – [Unexpected – if the event severity and/or frequency is not described in the investigator brochure (if applicable) or protocol].
5. Action taken with respect to study or investigational treatment or process (none, dose adjusted, temporarily interrupted, permanently discontinued, unknown, not applicable)

6. Whether medication or therapy taken (no concomitant medication/non-drug therapy, concomitant medication/non-drug therapy)
7. Whether the event is serious

Once an adverse event is detected, it should be followed until its resolution or until it is judged to be permanent, and assessment should be made at each visit (or more frequently, if necessary) of any changes in severity, the suspected relationship to the study treatment, the interventions required to treat it, and the outcome.

